5.3.1 Clinically notable vital signs

Table 5-8 presents the criteria that define notable abnormalities of vital signs data.

Table 5-7	Clinically notable vital signs
-----------	--------------------------------

Vital sign variables	Notable criteria
Systolic BP (mm/Hg)	160 or higher (hypertension stage 2)
Diastolic BP (mm/Hg)	110 or higher (hypertension stage 2)

5.3.2 Steroid conversion factors

Steroids will be displayed using prednisone equivalent body weight adjusted doses. The doses displayed in the following table are considered equivalent. To determine prednisone equivalent doses, doses will be multiplied by the conversion factor shown in Table 5-8. To adjust the dose, the body weight measured closest to the start of a steroid dose will be used (from vital signs eCRF).

WHO drug code	Preferred Term Corticosteroid	Equivalent Dose [mg]	Conversion Factor
000447xx	Prednisone	5	1
000162xx	Prednisolone	5	1
000496xx	Methylprednisolone	4	1.25
012428xx	Meprednisone	4	1.25
001867xx	Prednylidene	5 5/7	0.875
000319xx	Triamcinolone	4	1.25
000146xx	Cortisone	25	0.2
000286xx	Hydrocortisone	20	0.25
002131xx	Fludrocortisone	2	2.5
000085xx	Betamethasone	0.75	20/3
000664xx	Paramethasone	2	2.5
000160xx	Dexamethasone	0.75	20/3
008827xx	Deflazacort	6	5/6

Table 5-8 Steroids conversion factors

5.4 **Definition/Derivation of Efficacy Variables**

All efficacy endpoints regarding biopsy described will be summarized based on the central pathologists' evaluation of all biopsy readings. If the central pathologist's evaluation is missing, then the local evaluation will be used.

All acute rejections determined by local biopsy reading are recorded in the clinical database on the Liver allograft rejection and Liver allograft biopsy eCRFs. Central pathological reading will be electronically trasnferred.

5.4.1 Efficacy endpoint derivations based on central readings

Humoral rejection/AMR

A rejection is considered as a humoral rejection if:

- MI.MITEST = "AAMR" and MI.MIRESC = "Y"; AND
- Reason for biopsy = "Suspicion of rejection" on Liver Allograft Biopsy eCRF page.

Date of AMR will be MI.MIDAT_RAW when MI.MITEST = "AAMR" and MI. MIRESC= "Y".

AR

A rejection is considered an AR if:

- Antibody-mediated rejection (see above); **OR**
- MI.MITEST = "ATCELL" and MI. MIRESC = "Y"; AND
- Reason for biopsy = "Suspicion of rejection" on Liver Allograft Biopsy eCRF page.

Date of AR will be min(MI.MIDAT_RAW when MI.MITEST = "AAMR", MI.MIDAT_RAW when MI.MITEST = "ATCELL") when MI. MIRESC= "Y".

BPAR

A rejection is considered a BPAR if:

- AR (see above); AND
- MI.MITEST = "RAITOT" and MI.MIRESN \geq 3; AND
- Reason for biopsy = "Suspicion of rejection" on Liver Allograft Biopsy eCRF page.

Date of BPAR will be date of MI.MIDAT_RAW when MI.MITEST = "RAITOT" and MI.MIRESN \geq 3.

Steroid resistant AR

A rejection is considered a steroid resistant AR if

- AR (see above); AND
- Was the rejection steroid resistant = "Yes" from Liver Allograft Rejection eCRF page Date of steroid resistant AR will be the date of AR (see above).

Antibody treated AR

A rejection is considered an antibody treated AR if

- AR (see above); AND
- Was antibody treatment administered = "Yes" from Liver Allograft Rejection eCRF page

Date of antibody treated AR will be the date of AR (see above).

Steroid treated AR

A rejection is considered an steroid treated AR if

- AR (see above); AND
- Were steroids administered = "Yes" from Liver Allograft Rejection eCRF page

Date of steroid treated AR will be the date of AR (see above).

Steroid resistant BPAR

A rejection is considered a steroid resistant BPAR if

- BPAR (see above); AND
- Was the rejection steroid resistant = "Yes" from Liver Allograft Rejection eCRF page Date of steroid resistant BPAR will be the date of BPAR (see above).

Antibody treated BPAR

A rejection is considered an antibody treated BPAR if

- BPAR (see above); AND
- Was antibody treatment administered = "Yes" from Liver Allograft Rejection eCRF page

Date of antibody treated BPAR will be the date of BPAR (see above).

Steroid treated BPAR

A rejection is considered an steroid treated BPAR if

- BPAR (see above); AND
- Were steroids administered = "Yes" from Liver Allograft Rejection eCRF page

Date of steroid treated BPAR will be the date of BPAR (see above).

5.4.2 Efficacy endpoint derivations based on local readings

AR

A rejection is considered an AR if:

• Primary clinical diagnosis = "Acute rejection" or "Acute and chronic rejection from Liver Allograft Rejection eCRF page.

Date of AR will be "date rejection was first suspected" from the Liver Allograft Rejection eCRF, or if missing, the first available date of the biopsy of the particular rejection episode from the Liver Allograft Biopsy eCRF page.

Treated AR (tAR)

A rejection is considered a tAR if:

- Acute rejection (see above); AND
- Was anti-rejection therapy administered = "yes" from Liver Allograft Rejection eCRF page

Date of tAR will be the date of the corresponding AR (note: tAR is the subset of AR).

BPAR

A rejection is considered a BPAR if:

- Histological Evidence of Acute Rejection = "Yes" and of Acute and Chronic Rejection = "Yes" from Liver Allograft Biopsy eCRF page; AND
- Total RAI score ≥ 3 and Reason for biopsy = "Suspicion of rejection" from Liver Allograft Biopsy eCRF page.

Date of BPAR will be the date of the corresponding AR (note: BPAR is a subset of AR).

Treated BPAR (tBPAR)

A rejection is considered a tBPAR if:

- Biopsy-proven acute rejection (BPAR) (see above) AND
- Was anti-rejection therapy administered = "yes" from Liver Allograft Rejection eCRF page

Date of tBPAR will be the date of the corresponding AR (note: tBPAR is the subset of AR).

Death

Death will be recorded at either Study Completion, Follow-up, or as the outcome of an AE/Infection, if it occurs.

The date of Death will be the date of death recorded on the Disposition eCRF.

Graft loss

The allograft will be presumed to be lost on the day the participant becomes newly listed for a liver allograft or the day the participant is re-transplanted or dies due to liver failure.

Graft losses will be identified from Graft Loss CRF page.

Loss to follow-up

A lost-to-follow-up participant is one who discontinued the study and did not experience BPAR, graft loss, or death, and whose last day of contact is prior to the day of the lower limit of the (Month 12 or 24) visit window. The date of loss to follow-up is the last contact date.

Composite efficacy failure

The date of composite efficacy failure will be the earliest non-missing date among the individual components of the composite endpoint.

For the composite endpoints and each individual endpoint, if the date of the event is not available, then the event will be included in listings and the simple proportion efficacy tables, but excluded from survival analysis.

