8.3.4 Death

In the event of participant death, the SAE leading to death should be reported to the Novartis CMO & PS department within 24 hrs. The events leading to the death should be entered on the appropriate CRF capturing Adverse Events. The death as reason for discontinuing study should be indicated on the Study Completion CRF.

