2.1 Data analysis general information

Due to the early termination of the study, the analysis plan has been modified and may be different from the Protocol.

The primary analysis will be performed after all participants have completed the Month 12 visit, or prematurely discontinued study before Month 12. These analyses will be performed by a Contract Research Organization, ICON. Interim analyses, detailed in Section 2.13, will be performed also by ICON.

The following general data conventions will apply:

- Cut-off day is defined as the latest study day before or up to which data will be used in the • analysis. Note that safety data collected during the Safety Follow-up period after EOS is reported to Novartis/Safety and will be included in relevant analyses.
- Descriptive statistics will be calculated based on observed values. Missing values will be • presented separately for each parameter or category. Categorical data will be presented as frequencies and percentages. For continuous data, n (sample size), mean, standard deviation, median, 25th and 75th percentiles, minimum, and maximum will be presented.
- BPAR will be based on centrally blinded adjudicated data. All other efficacy • endpoints will also be based on central

lab data.

- AE, SAE, Infection, Serious Infection (including malignancies), CMV information, and • EBV information will be summarized based on all eligible collected events.
- All lab and vital sign tables will include data since baseline (liver Tx) but changes are calculated based on the day of randomization. All summaries are based on central lab data.

Novartis	
SAP	

- Efficacy and liver function analyses are based on all available data including those after study medication discontinuation or as a supportive analysis based only on on-treatment values. Participants are censored for the time-to-event analyses if they do not have an event. For on-treatment analysis, the censoring day is the date of discontinuation of study treatment (defined in Section 2.1.1); for the all-data analysis (regardless of on-treatment or off-treatment), the censoring day is the last contact day.
- Listings will only be provided for variables explicitly indicated in this SAP. Listings will include all available data.

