5.2 Imputation rules

Although not the rule, partially or completely missing dates occur. Known dates with this issue are the start date on the Medical History eCRF page, start and end dates on the Concomitant Medications eCRF page, or Surgical and Medical Procedures page eCRF page, and occasionally the start and end dates on the Adverse Events eCRF.

Any date incompletely reported is split into its day, month, and year components. In SAS, a numerical date value can only be defined if all these date components are known; incomplete dates are to be handled as text strings (character-type variables); as such, they could not be easily processed. An imputation rule for incomplete dates will be performed.

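### A known failure with no recorded date leaves the supplementary Kaplan-Meier analysis, and death has only one permitted date source, so a death without a Disposition date could understate an arm's failure rate

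*SAP*

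**What the plan says.** - **Undated events.** SAP 5.4.2 ends with a rule for the composite and for each single endpoint. An event with no available date stays in the listings and the "simple proportion efficacy tables, but excluded from survival analysis".
- **Deaths.** The section first allows several sources: "Death will be recorded at either Study Completion, Follow-up, or as the outcome of an AE/Infection, if it occurs". It then allows one source for the date: "The date of Death will be the date of death recorded on the Disposition eCRF". No fallback follows. For locally read acute rejection, the same section does give one (the first biopsy date of the episode).
- **Composite.** "The date of composite efficacy failure will be the earliest non-missing date among the individual components of the composite endpoint". Graft loss includes the day of new listing, "or the day the participant is re-transplanted or dies due to liver failure".
- **Date imputation.** SAP 5.2 accepts that "partially or completely missing dates occur", but its rules cover adverse event and concomitant medication dates only.
- **Use of Kaplan-Meier.** SAP 2.4.5 plans it as a supplementary analysis of the composite and of BPAR, with 95% confidence intervals for the arm differences. The primary analysis (SAP 2.4.2) is a Poisson model.
- **Recording of death.** Protocol 8.3.4: "The death as reason for discontinuing study should be indicated on the Study Completion CRF".

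**The concern.** Only a participant who has failed can meet the exclusion rule; an event-free participant never can. The rule therefore selects on outcome, and within an arm it can act in one direction only, by lowering the estimated failure rate.

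Death is the component most exposed, because it can be known from one page while its date may be taken only from another. Early termination makes this plausible. SAP section 1 says the study was terminated in September 2022. Protocol 9.1.6 has participants seen as soon as possible and treated as prematurely withdrawn. Protocol 10.1.3 continues SAE reporting for 14 weeks after the last CFZ533 dose and 12 weeks for tacrolimus. SAP 2.1 brings "safety data collected during the Safety Follow-up period after EOS" into the relevant analyses. A death in that window could thus be known and dated as an SAE after the completion page had been filled with another reason. If it falls before Month 12, the estimand in SAP 2.4.1 counts it, because that estimand disregards treatment and study discontinuation.

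At stake is a Kaplan-Meier estimate that could contradict the simple summaries reported beside it under SAP 2.4.5. SAP 2.4.4 plans no sensitivity analysis.

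**Working it through.** **Plan's own figure.** The documents give no number for this rule. The nearest stated figures are the probabilities of success in SAP Table 3-2. Exact binomial enumeration with Beta(1/3, 1/3) priors reproduces all 15 rows within 0.002 (for example 0.903 against the stated 0.904 at rates 0.11 and 0.103). They do not depend on event dates, so the rule leaves them unchanged.

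**When a failure drops out.** By the text, all three conditions must hold:
1. The death has no Disposition date.
2. The participant has no dated BPAR; otherwise the earliest-date rule keeps the composite event.
3. The participant has no dated graft loss; a liver-failure death recorded as graft loss is kept.

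**Inputs.** Arms of 48 and 32 and an expected control rate of 10% come from SAP 3.2. Day 358 as the end of the Month 12 window comes from SAP Table 5-1. The event counts are assumptions near the planned rate: k = 5 of 48 (CFZ533) and k = 3 of 32 (control). All event-free participants are assumed to be followed to Day 358. The number of undated failures, u, is not in the documents; u = 1 or 2 is used for illustration.

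**Formulas.** With no earlier censoring, the Kaplan-Meier failure rate is k/n. The SAP does not say whether an excluded participant is removed or censored:
- removed: (k − u)/(n − u)
- carried event-free to Day 358: (k − u)/n
- censored at last contact: between these two in the runs made

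| Case | CFZ533 (n = 48) | Control (n = 32) |
|---|---|---|
| All dated | 5/48 = 10.4% | 3/32 = 9.4% |
| u = 1 | 4/48 = 8.3% to 4/47 = 8.5% | 2/32 = 6.3% to 2/31 = 6.5% |
| u = 2 | 3/48 = 6.3% to 3/46 = 6.5% | 1/32 = 3.1% to 1/30 = 3.3% |

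One case costs 1.9 to 2.1 points in 48 and 2.9 to 3.1 points in 32. The standard errors with all events dated are 4.4 and 5.2 points, so one case is worth roughly half a standard error.

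**Arm difference (CFZ533 minus control).**
- All dated: 10.4 − 9.4 = +1.0 points
- One undated CFZ533 failure: −0.9 (removed) to −1.0 (carried to Day 358)
- One undated control failure: +4.0 (removed) to +4.2 (carried to Day 358)

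**Censoring day.** SAP 2.4.5 censors at the last contact day; SAP 5.5 censors at the last day of the analysis visit window. If exclusion means censoring, the SAP 5.5 rule would carry a participant known to have died as event-free to Day 358.

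**The case against.** The case for leaving the text alone has real substance.

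- **Safeguards exist.** A dated BPAR or graft loss keeps the composite event. Rejections are dated from biopsies, locally with a fallback, so the exposure is mainly through death. The Protocol wants every death on the Study Completion CRF, which I take to be the SAP's Disposition page. Protocol 9.1.1 also names death as a reason to complete that page early. A case therefore needs a recording gap or a death after the page was closed. This stands, and it makes cases rare.
- **No known problem on the source pages.** The pages SAP 5.2 lists as having date problems do not include Disposition, Graft Loss or biopsy. They do include adverse events, which is one of the proposed fallback sources. This stands, but an imperfect second source is still better than none.
- **Limited role.** Kaplan-Meier is supplementary and has no success criterion; the 15-point margin belongs to the Poisson posterior. SAP 2.4.5 also plans summaries of the composite and its components, so Kaplan-Meier is not the only check and a discrepancy would be visible. This stands.
- **The fix could bias the other way.** Adding deaths learned from post-study safety reporting, while survivors are censored at last contact, could push the estimate up. This stands and is why the fix below ties the death date to the follow-up window used for event-free participants.

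None of this supplies a reason to discard a failure that is known to have happened.

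**Conclusion.** The point holds as a minor, conditional one. The exclusion is written into the SAP, and death alone among the dated components has several recording sources but one date source. For each failure that meets all three conditions, that arm's supplementary Kaplan-Meier composite rate would be too low by about 2 points in 48 or about 3 in 32, and would disagree with the simple proportions. These sizes rest on the assumed counts and on complete follow-up to Day 358.

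A reader might infer more, which the documents do not support:
- **That every death recorded only as an adverse event outcome is lost.** The composite keeps it when another component is dated.
- **That the reported rate is too low.** No undated case is shown, and zero cases would mean no effect.
- **That the rule favours CFZ533.** The difference moves down or up according to the arm of the undated failure.
- **That the primary result is affected.** The SAP does not say that its exclusion reaches the Poisson model, whose follow-up formula does not use the event date.

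**What to change.** 1. In SAP 5.4.2, define the date of death as the earliest non-missing date of death on any page that records it: Disposition, Follow-up, or adverse event/SAE outcome. Apply this within the same Month 12 follow-up window used to censor event-free participants.
2. Keep any failure that is still undated as an event at a stated conventional date, for example last contact date + 1 day. The exact convention is a matter of choice; it should be fixed in advance.
3. Delete the clause that takes undated events out of the survival analysis. The question of whether they are removed or censored then no longer arises.
4. Reconcile the Kaplan-Meier censoring day in SAP 2.4.5 with that in SAP 5.5.

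The cost is a few lines of text and derivation code. SAEs in the safety follow-up go to the safety database (Protocol 9.2), so some reconciliation with it may be needed. If no undated death exists, items 1 to 3 leave death handling in the Kaplan-Meier analysis unchanged, apart from any case where the pages give different dates.

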5.5 Statistical models

Novartis

SAP

Randomization seed for random functions utilized in all analyses is set to 5332202.

For the posterior probability simulation, the number of iteration is set to 10000.

For Kaplan-Meier estimates and related analyses, the censoring day is the last day of the associated analysis visit window.

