2.4.5 Supplementary analyses

Kaplan-Meier (KM) estimates of events rates of composite efficacy failure and BPAR censored at Month 12 will be respectively summarized and presented graphically. In addition, participants who have not experienced composite efficacy failure, are lost to follow-up, or do not attend the Month 12 visit after treatment discontinuation will be censored with the censoring time defined by the last contact day.

For Kaplan-Meier estimates, Greenwood's formula will be used to estimate the variance and to derive 2-sided 95% Z-test based confidence intervals for the difference between a CFZ533 arm and the Control arm. The confidence interval will be constructed as:

$$(r_{T_i} - r_C) \pm Z_{\alpha/2} * SE_{d_i},$$

where

 r_{T_i} = Kaplan-Meier estimate of the failure rate for CFZ533 arm up to 12 months, i = 1, 2,

 r_c = Kaplan-Meier estimate of the failure rate for the control arm up to 12 months,

$$SE_{d_i} = \sqrt{SE_{T_i}^2 + SE_C^2}, i = 1, 2,$$

 SE_{T_i} = Estimated standard error for CFZ533 arm based on Greenwood's formula, i = 1, 2,

 SE_c = Estimated standard error for the control arm based on Greenwood's formula, and $\alpha = 0.05$.

Summaries of the composite efficacy failure and its individual components will be provided. Acute rejection events will be summarized by treatment and severity for central and local assessment, respectively. Histological evidence and pathological assessment of liver allograft biopsies will be provided in the listings for central and local assessment, respectively.

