* For all Month 12 analyses, the end of visit window of Month 12 visit is Day 358, instead of Day 372.

Under this window schema, multiple records of a participant are re-aligned into the same visit as follows:

- For post-randomization continuous values (except for CFZ533, TAC, and MMF trough level measurements and liver tests), for a given participant, if multiple numeric measurements for a given variable are reported in the same visit window (e.g., Month 6), then the measurement closest to the target visit day will be taken; if tie, take the earlier measurement. For screening visit, the target day is day of transplant – 1; for baseline, day of transplant; for randomization, start of study drug (Day 1); for other visits, the midpoint of the visit window.
- For trough levels, the last value observed within a visit window is taken.

- For liver tests (bilirubin, SGOT, SGPT, GGT, and alkaline phosphatase), the following algorithm is applied:
 - a. If an acute rejection occurs within a visit window with multiple liver tests reported, the time of the event is the date rejection first suspected, and the liver test to be summarized are the closest to that event (if tie, take the earlier one)
 - b. If no rejection occurs, the assessment closest to the target day is taken.
- For categorical values, the worst value of all records observed in the visit window is used.

For parameters which are not collected at every scheduled visit

, visit windows defined in Table 5-1 will be combined using the following rules for an applicable visit post randomization: "lower limit" of the combined window= "upper limit of prior applicable visit" + 1, "upper limit" of the combined window = "target day of current visit" + integer part of [("target day of next applicable visit" – "target day of current visit")/2]. For example, if a parameter is measured only at Randomization, Day 29 (Month 1), Month 3, Month 6, and Month 12, the combined Day 29 (Month 1) visit window will be from Day 2 to Day 50 (= Day 22 + interger part of [(78 - 22)/2]), Month 3 will extend from Day 51 to Day 120 (= Day 78 + interger part of [(162 - 78)/2]), etc.. If more than one assessment falls into the combined window, the rules defined above handling multiple records are applied.

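### SAP 5.5 sets a Kaplan-Meier censoring day that conflicts with the last-contact rule in SAP 2.4.5, SAP 2.1 and Protocol 12.4.4; taken literally, it understates failure when participants leave early

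*SAP*

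**What the plan says.** The SAP states the censoring day for time-to-event analyses in several places.

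- SAP 5.5 (Statistical models), on Kaplan-Meier analyses: "the censoring day is the last day of the associated analysis visit window". It makes no exception for participants who leave earlier.
- SAP 5.1, note to Table 5-1, fixes that day for Month 12: "For all Month 12 analyses, the end of visit window of Month 12 visit is Day 358, instead of Day 372".
- SAP 2.4.5 (Supplementary analyses) describes the Kaplan-Meier estimates of composite failure and BPAR as censored at Month 12. It then adds that participants who are event-free, are lost, or miss Month 12 after stopping treatment "will be censored with the censoring time defined by the last contact day". Protocol 12.4.4 has the same rule.
- SAP 2.1 covers time-to-event analyses generally. For the all-data version, "the censoring day is the last contact day". The other version has its own date: "For on-treatment analysis, the censoring day is the date of discontinuation of study treatment".
- SAP 5.4.2 defines a lost participant as one with no event who left the study and "whose last day of contact is prior to the day of the lower limit of the (Month 12 or 24) visit window" (Day 303 for Month 12 in Table 5-1). It adds: "The date of loss to follow-up is the last contact date".

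No section ranks these rules. SAP 4 reports no change to the protocol-specified analyses. SAP 2.1 says only in general terms that the plan may differ from the protocol because of early termination.

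**The concern.** A participant lost under SAP 5.4.2 was last seen on Day 302 at the latest. Read literally, SAP 5.5 keeps that person in the risk set, event-free, until Day 358. That is at least 358 − 302 = 56 days that nobody observed, and far more for someone who left in the first months. Last-contact censoring removes the person from the risk set when observation ends, which is the reason for using Kaplan-Meier with incomplete follow-up.

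Two outputs are at stake: the Kaplan-Meier failure rate in each arm, and the 95% Greenwood interval for the difference between each CFZ533 arm and control. If loss differs between arms, the difference is biased as well as the rates. A contract research organization runs the analyses, so a programmer could follow either section and claim to have followed the SAP.

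**Working it through.** The documents state no Kaplan-Meier figure to reproduce. The check compares the two rules on the same data.

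**1. Algebra.** If every event-free participant is censored at Day 358, nobody leaves the risk set before then except by having an event. The product over event times telescopes, so failure = 1 − (n − d)/n = d/n, the crude proportion. Greenwood's variance becomes (d/n)(1 − d/n)/n, as if all n had been followed in full.

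**2. Worked example.** Assumed data: n = 48 (planned CFZ533 arm size, SAP 3.3); events on Days 30, 60, 120, 200 and 300; ten lost on Days 20, 50, 80, 110, 140, 170, 210, 230, 260 and 290; 33 complete.

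- *Last contact.* Numbers at risk at the five events are 47, 45, 42, 39 and 34. S = (46/47)(44/45)(41/42)(38/39)(33/34) = 0.8835, so failure is 11.7%. The Greenwood sum is 1/(47·46) + 1/(45·44) + 1/(42·41) + 1/(39·38) + 1/(34·33) = 0.00311. SE = 0.8835 × √0.00311 = 4.9%.
- *SAP 5.5, literal.* Failure is 5/48 = 10.4%. SE = √(0.104 × 0.896/48) = 4.4%.
- *Earlier of last contact and Day 358.* Failure is 11.7%, SE 4.9%, identical to last contact.
- *Window end taken as the end of the window containing last contact.* Failure is 11.5%, SE 4.9%.

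**3. Expected size under the literal reading.** Assumptions: a share p is lost uniformly over the 12 months, independently of outcome, with constant hazard. Let F be the true 12-month rate and h = −ln(1 − F). The literal estimate is (1 − p)F + p(1 − F/h). For F = 10% (the control rate expected in SAP 3.2), h = 0.1054 and 1 − F/h = 0.0509:

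- p = 10%: 0.0900 + 0.0051 = 9.5%
- p = 20%: 0.0800 + 0.0102 = 9.0%
- p = 30%: 0.0700 + 0.0153 = 8.5%
- p = 0: 10.0%, no difference between the rules

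**4. Simulation check.** Last contact uniform over Days 1–303, 1,500 datasets per scenario, n = 48, true rate 11%, constant hazard. Mean last-contact estimate against literal 5.5:

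- 5% lost: 11.0% against 10.7%
- 10% lost: 10.9% against 10.3%
- 20% lost: 10.9% against 9.7%
- 30% lost: 11.0% against 9.1%
- 50% lost: 11.2% against 8.1%

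With half of the cumulative hazard in the first 90 days, the gap shrinks to 0.9 points at 20% lost and 2.3 points at 50%. The literal estimate never exceeded the last-contact estimate in any dataset.

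**5. Between arms.** If both arms had a true 10% rate but 30% were lost in one and 10% in the other, step 3 gives 8.5% against 9.5%. That is an apparent difference of about 1 point in favour of the arm with more loss. With equal rates and equal loss the bias in the difference cancels, but the standard error is still too small.

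**The case against.** The best defence is that SAP 5.5 states an administrative cap. SAP 2.4.5 has two tiers: estimates are censored at Month 12, and early leavers are also censored at last contact. The first tier needs a calendar day, because Table 5-1 offers two ends for the Month 12 window (372, or 358 for Month 12 analyses), and 5.5 supplies it. The more specific sections all agree on last contact. This reading is plausible, and under it there is no bias. But 5.5 says what the censoring day is, not what it may not exceed, and nothing elsewhere calls it a cap. The conflict in the text therefore stands, while the bias is conditional on the literal reading.

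The effect is also modest beside sampling error: 0.5 to 1.5 points at a 10% rate, against a standard error of 4.4 to 4.9 points in the example. That stands too. However, this error has a fixed direction and is avoidable.

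Three stronger conclusions are tempting but not supported:

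- *That the trial's success decision is affected.* It rests on the Poisson posterior in SAP 2.4.2, which has its own follow-up time and does not use 5.5.
- *That Kaplan-Meier is the only efficacy analysis using off-treatment data.* SAP 2.1 bases efficacy analyses on all available data, including after discontinuation. SAP 2.4.5 also plans summaries of the composite and its components, and SAP 5.4.2 mentions simple-proportion tables.
- *That early termination shows heavy loss before Month 12.* The documents give no share. By 28 February 2021, 59 participants had been randomized, about 18 months before termination in September 2022. The protocol also follows participants to Month 24 after they stop treatment.

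**Conclusion.** The SAP contains conflicting censoring rules for the same Kaplan-Meier analysis and does not say which governs. Under the literal 5.5 rule, failure is understated whenever participants at risk leave before later events occur, and precision is overstated. Under the cap reading nothing is lost.

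For the literal reading, the expected shortfall is about 0.5, 1.0 and 1.5 points at a true 10% rate with 10%, 20% and 30% lost. It is larger at higher event rates and smaller if events come early. These figures rest on assumed loss shares, uniform and independent loss, and constant hazard; none comes from the documents. The consequence is confined to the supplementary Kaplan-Meier estimates and their intervals. The correction should be made, but it does not bear on the success criterion.

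**What to change.** Replace the SAP 5.5 sentence with: censoring day = the earlier of the last contact day and the last day of the associated analysis visit window (Day 358 for Month 12); for on-treatment analyses, the earlier of the end of study treatment and the last day of that window.

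This keeps the cap if that was the intention, agrees with SAP 2.4.5, SAP 2.1, SAP 5.4.2 and Protocol 12.4.4, and returns 11.7% in the worked example. The cost is one sentence in the SAP and a check that the programmed censoring date follows it. No new data or analysis is needed.
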